5.2.4 Mentor/Advisor Training

Once mentors /advisors are recruited and deemed eligible they will be scheduled to receive 8- 10 hours of structured virtual training that will be conducted via the Peer Mentor University platform. The virtual training is expected to be completed in no more than 3 weeks (+/- 1 week) from enrollment. Once this virtual training is complete, the mentor / advisor will then be trained on how to access and use the Mentor1to1TM platform to make the required mentoring contacts via telephone (mentors to mentees only) and contacts via SMS messaging (required for all advisor and mentor contacts). SMS messaging can be used as a supplementary resource for mentor to mentee contacts). Mentors will receive an automated

Version 6: 12/22/2022

email from InquisitHealthTM to establish an account which prompts them to proceed with platform training.

Mentor/advisor education material specific to SCD have been created for use with the Mentor1to1TM platform and was prepared in line with evidence-based "Elements of Effective Practice for Mentoring" prepared by the National Mentoring Partnership (Elements for Effective Practice for Mentoring, 2015) following the guidelines provided in Chronic Disease Self-Management (CDSM) program.

Mentor contact via telephone calls (and supplemental SMS messaging) will be monitored and evaluated through the Mentor1to1TM Administrator Platform. Calls between mentors and mentees will be recorded and monitored periodically for quality assurance. All transcripts of mentor—mentee supplemental communication via SMS messaging through the platform will also be available for review for quality assurance by platform administrator.

Mentors will initially be assigned 1 mentee and will complete 1-2 calls with their mentee. These initial calls will be monitored retrospectively by the platform administrators or designee to determine adherence to talking points, quality of mentorship, and to determine any areas of improvement for the mentor. Based on completion of at least four Mentor-Mentee calls, Mentors will be evaluated and assigned additional mentees (up to a maximum of 3) or a plan for improvement in mentoring skills.

- Mentors are expected to have at least 4 calls within a calendar month with mentees during the first 3 months after enrollment.

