6.3 EA-SCD Participant Level Assessment Calendar

EA-SCD Participant Level Assessment Calendar																								
Study Month	Screening																							
	All Sites	Peer Mentor Sites Only	Baseline	3	6	9	12	15	18	21	24	27	30	33	36	39	42	45	48	51	54	57	60	Off Study
Eligibility Screening	•																							
Informed Consent / Assent	•																							
Demographics/Disease Characteristics ^a	•																							•
Mentor Matching ^b		● ^g																						
Acute and Ambulatory Care Visit Data Collection ^c			•	•	•	•	•	•	•	•	•	•	•	•	•	•	•	•	•	•	•	•	•	•
Transition Education Intervention Q3			• h	•	•	•	•	•	•	•	•	•	•	•	•	•	•	•	•	•	•	•	•	•
PedsQL-SCD Module			● h		•		•		•		•		•		•		•		•		•		•	•
MOS-SSS			● h		•		•		•		•		•		•		•		•		•		•	•
TIP-RFT			• h		•		•		•		•		•		•		•		•		•		•	•
ASCQ-ME QOC			• h		•		•		•		•		•		•		•		•		•		•	•
Health Care Transition Feedback Survey for Youth/Young			• h				•				•				•				•				•	•
ST3P-Up App	Downloade		Download	•	•	•	•	•	•	•	•	•	•	•	•	•	•	•	•	•	•	•	•	•

- a Demographic information collected at baseline will be re-assessed at end of study for updates and/or changes
- b During screening, EA-SCD subjects are required to provide their day/time availability for peer mentoring calls to facilitate mentor matching. These subjects MUST be matched to a mentor prior to administering baseline surveys
- c Ambulatory and acute care visits will be collected for the preceding 12 months (a month is defined, numerically, as 30.4375 days, and visit windows are based on the date of enrollment). Ambulatory visits will include visits within the healthcare setting, primary care visits, and virtual visits via telephone ONLY. Acute care visits may include, but are not limited to ED, urgent care, day hospitals, infusion centers, and hospital admissions.
- d Study visits will occur with a +/- 4 weeks window for q3mo visits. EA-SCD subject must be seen by their SCD provider during these visits. However, these visits may occur in other locations within the healthcare setting where SCD care is provided or virtually as long as required structured and targeted transition education is provided

Version 6: 12/22/2022

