e - ST3P-UP App contains "Who, What, Where, When" Sickle Cell Transition Education Modules that are required for 3-month visits. If app is not available, the education modules are provided to the sites in the QI Change Package and via PowerPoint from the DCC. Alternatively, sites can utilize any standard SCD education module.

- f Patients are encouraged but not required to download the ST3P-UP App. Directions to access the ST3P-UP app and instructions for use will be provided to participants by local site Transition Coordinators. Transition Coordinators are encouraged to use study- provided tablets and/or iPads to facilitate follow-up visit adherence communication and for structured transition education.
- g For PM sites, mentee availability should be captured in the REDCap database at the time of consent. For subjects with delayed enrollment, confirmation of availability should be revisited at the time of Mentor-Mentee matching.
- h Every effort should be made to complete the baseline survey within a healthcare setting but if administration occurs via survey link, this must be provided to the participant within 72 hours from the date of consent (for the STE arm) or from the date of match (for the PM arm). The survey link will expire within 2 weeks of receipt. If the survey remains incomplete after two weeks, please discontinue efforts to contact the participant for completion of the baseline survey.

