10.1.2 Enrollment Date

EA-SCD Participants:

The date the baseline survey is administered to a subject (either within a healthcare setting or via survey link).

For participants on the PM arm, administration of the baseline survey and completion of the enrollment CRF occurs after confirmation of mentor matching from the DCC (see study calendar 6.3).

Mentor and Advisor Participants:

The date the participant completes all training activities. For mentors, this is the date the participant completes practice call 2. For advisors, this is the date the participant completes Peer Mentor University training.

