10.5.5 Secondary Analysis

EA-SCD PRO's will be analyzed quantitatively using linear mixed models for repeated measures. The models will include fixed factors for baseline scales, the site size stratification factor, treatment arm, assessment time point, and the treatment arm by time point interaction. Random factors will include investigational site and subject within site to account for correlation in responses within individual sites and within the same subject. Model-based estimates of PRO scores will be used to estimate percentage change between the treatment arms. Additionally, PRO will be analyzed using survival analysis techniques. For each EA-SCD participant, the time from baseline to a 10% worsening (TTW) in the scale will be calculated. For EA-SCD participants not experiencing a 10% worsening, TTW will be censored at the last patient reported outcome assessment. TTW will be analyzed using Kaplan-Meier techniques and Cox proportional hazards models. The

proportional hazards models will include the same factors as described for the primary analysis. Planned sensitivity analysis will be conducted to evaluate time to worsening for worsening thresholds ranging from 10% to 30%. The repeated measures and survival analyses of the EA-SCD PRO's will also include supportive and sensitivity analyses to account for potential baseline confounders as previously described in the primary analysis. EA-SCD satisfaction with transition services will be summarized descriptively.

Intervention fidelity will be analyzed descriptively. A CONSORT-type diagram will be provided, including a summary of all mentors who consented, had a background check, passed the background check, completed practice call 1, completed Peer Mentor University online training, completed practice call 2, and were matched with at least one EA-SCD. Timelines for mentors and EA-SCDs on the PM arm will be summarized descriptively. Frequency of mentor contacts will be analyzed descriptively in terms expected contacts per protocol versus actual. This will include calls placed (mentor to EA-SCD), calls answered (EA-SCD to mentor), messages sent (mentor to EA-SCD), and messages received (EA-SCD to mentor).

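### Nothing in the plan holds the first mentoring call until the baseline PRO survey is complete, so some PM-arm baselines may be answered after mentoring has begun

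*Combined protocol and SAP*

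**What the plan says.** - **Order on the PM arm.** The calendar (6.3 note b) states: "These subjects MUST be matched to a mentor prior to administering baseline surveys". Section 10.1.2 agrees: "administration of the baseline survey and completion of the enrollment CRF occurs after confirmation of mentor matching from the DCC".
- **Enrollment date.** It is defined in 10.1.2 as "The date the baseline survey is administered to a subject (either within a healthcare setting or via survey link". The trigger is administration. If a link goes unanswered for two weeks, note h tells sites to stop pursuing it, so completion is not a condition of enrollment.
- **Survey clocks.** Under 6.3 note h, a link must be provided "within 72 hours from the date of consent (for the STE arm) or from the date of match (for the PM arm". For both arms, "The survey link will expire within 2 weeks of receipt". Clinic completion is preferred: "Every effort should be made to complete the baseline survey within a healthcare setting".
- **Call clock.** Sections 5.2.4 and 5.2.5 and 6.2 note c agree: "Mentors are expected to have at least 4 calls within a calendar month with mentees during the first 3 months after enrollment".
- **Start of intervention.** Section 4.2 asks for registration and consent at the participant level. It does not mention the baseline survey.
- **Use of the score.** In 10.5.5, for the repeated-measures PRO analysis, "The models will include fixed factors for baseline scales". The same section measures time to a 10% worsening from baseline.

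**The concern.** A baseline covariate should be measured before the intervention can act on it, and in the same way in both arms. Here the PM survey window and the period in which calls are expected both open at enrollment, and no rule orders them. STE participants have no mentor calls, so any overlap falls on one arm only.

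The scale most exposed is the MOS-SSS. Section 1.2 presents peer mentoring as acting on isolation and the social side of transition, and 5.3.4 describes the MOS-SSS as a measure of social support. If the first calls raise the reported score, adjusting for it removes part of the effect being estimated. On scales where higher is better, a raised reference also brings the 10% worsening threshold closer. Both would count against PM on the patient-reported objective in 2.2.1. Sections 10.5.4 to 10.5.6 contain no rule or sensitivity analysis for this.

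**Working it through.** The plan gives no figure on this point. Its sample-size figures concern the primary endpoint and do not enter.

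**1. Can a call precede the completed survey?** Side by side:
- Section 10.1.2 dates enrollment at administration of the survey.
- Section 6.3 note h allows up to 14 days from receipt of a link to complete it.
- Section 5.2.4 counts expected calls from enrollment.
- Section 4.2 sets no survey condition on starting the intervention.

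The overlap is permitted. It is not prescribed: no section dates the first call, and four calls within a calendar month carry no spacing rule.

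**2. How many calls could fit?** Inputs: at least 4 calls a month (5.2.4), a month of 30.4375 days (6.3 note c), a link life of 14 days and a sending limit of 72 hours (6.3 note h). With even spacing at the minimum rate, calls = 4 × days / 30.4375.
- From enrollment to link expiry: 4 × 14 / 30.4375 = 1.8.
- From match to link expiry, if calls could start at the match: 3 + 14 = 17 days, and 4 × 17 / 30.4375 = 2.2.
- Clinic completion on the enrollment date, or a first call made after completion: 0.

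Over 30 months the minimum expected total is 12 + 27 × 2 = 66 calls, so 1.8 calls is about 15% of the first 12 and about 3% of the whole.

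Section 5.2.4 does not say whose enrollment starts the count, and 10.1.2 defines mentor enrollment separately (at practice call 2). On that reading the calls are not tied to the mentee's survey at all.

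**3. Effect on the mixed model.** Let p be the share of PM participants answering after a call, d the mean lift among them, and b the slope of follow-up on baseline. The adjusted arm effect loses about p × b × d. None of these is in the documents. Assume b = 0.3–0.7 and d = 1–3 points on a 0–100 scale:
- p = 0: no loss.
- p = 0.25: 0.25 × 0.3 × 1 = 0.08 to 0.25 × 0.7 × 3 = 0.53 points.
- p = 1 (everyone): 0.3 × 1 = 0.3 to 0.7 × 3 = 2.1 points.

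In relative terms, if a fraction f of the eventual effect is already present in those participants, the loss is p × b × f. With b = 0.7 and f = 0.25 this is 17.5% at p = 1 and 4.4% at p = 0.25.

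**4. Effect on time to worsening.** As an illustration, take a participant whose score before mentoring is 60. The threshold is 0.9 × 60 = 54.0. If the recorded baseline is 63, it is 0.9 × 63 = 56.7, which is 3.3 rather than 6.0 points below the level before mentoring.

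**5. Primary endpoint.** Its baseline covariate is acute care visits in the 12 months before enrollment (6.4.2, 10.5.4). Late survey completion changes neither that count nor the enrollment date.

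**The case against.** Most of the case on the other side is sound, and it limits the point. A reader might infer more from these sections than they support:

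- **That the baseline may be taken up to two weeks after mentoring starts.** The two weeks run from receipt of the link. A match is not mentoring: it is a screening step (6.4.1), and 5.2.4 dates the mentoring role from the first call.
- **That every PM baseline is a post-intervention score.** A score given after the match but before any call reflects knowledge of the match, not mentoring. Sites are randomized before activation and the study is unblinded (4.2), so both arms answer after allocation. Those at risk are PM participants who use the link, answer late and have an early call. Clinic completion is preferred.
- **That STE participants answer at consent while PM participants answer late.** STE links have the same 72-hour sending limit and the same two-week life; only the starting event differs.
- **That the PM survey should move to consent.** Enrollment is the survey date, and it sets the rate denominators (10.3.1) and the analysis population (10.4). Moving the survey would put the unmentored wait and consenters who are never matched into the analysis, or require a new enrollment definition. Matching can be slow enough to need reconsent (3.2.1, criterion 8), so PM baselines would also age. Surveying near the match is defensible.

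The direction of bias assumes that early calls help, and one or two calls are less likely to move ASCQ-Me QOC, which rates care received (5.3.2). The synopsis also concedes that the PM comparator cannot be assessed quantitatively as originally planned, although 10.5.5 still specifies the PRO comparison by arm.

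What remains is that the survey and call rules, as written, allow a one-arm overlap and nothing in the analysis plan detects it.

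**Conclusion.** The point holds in a limited form. Some PM participants who answer by link may complete the baseline after about one or two calls, and no STE participant can. The 1.8-call figure assumes that calls start at enrollment and are evenly spaced at the minimum rate; the actual number could be zero or higher.

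If early mentoring helps, the bias runs against PM in the secondary PRO analyses. It is probably modest, but its size cannot be determined from the documents, because the share affected, the early lift and the slope are all unstated. If early contact lowered scores, the sign would reverse. The primary endpoint is essentially untouched. This is a cheap improvement to a secondary objective, not a threat to the trial's main comparison.

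**What to change.** **Conduct.** In 6.3 note h and 10.1.2, with matching text in 5.2.4 and 5.2.5, keep the survey after the match. State that the first mentor–mentee call does not take place until the baseline survey is completed or its two-week link has expired. Record the survey completion date and the first-call date. The platform already tracks calls, but 5.3 allows paper surveys and no section says that completion dates are kept.

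**Analysis.** In 10.5.5, flag any baseline completed after the first call. Add a sensitivity analysis of the PRO models that treats flagged baselines as missing and uses the multiple imputation already planned in 10.5.6. Complete-case deletion would not do, since it would remove PM participants only, and selectively those with early calls. This analysis is useful even for participants already enrolled, provided the dates can be recovered.

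**Cost.** Short text changes, one date field and one flag. For slow link responders the first call may be delayed by up to about two weeks, and the call counts used to define deviations in 5.2.4 and 5.2.5 would need to allow for that. The imputation rests on a missing-at-random assumption and applies to one arm only, so it should remain a sensitivity analysis.

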10.1.3 Off Study Date

For All Participants:

The date the subject terminates participation on the study or is removed from the study per the criteria in Section 7.1.

10.2 Sample Size and Accrual

Sample size calculations are based on the primary endpoint of acute care utilization visits per year (at the EA-SCD participant level). Utilizing a randomized cluster design, seven clinical sites will be randomized per arm. The sample size calculation strategy is to calculate the required minimum sample size based on an individual patient randomized design, and then inflate the sample size based on cluster randomized considerations.⁵⁴ A conservative estimate of the average acute care utilization rate for EA-SCD is 6 acute care visits per year based on data for North Carolina reported by the RuSH population surveillance project.⁴ In South Carolina, the acute care utilization rates among 18-30 y with SCD was reported as 7.17 (95% CI 6.34-7.99).55 At Atrium Health (formerly known as Carolinas Healthcare System), 295 EA-SCD had 1972 emergency department visits and 221 hospital admissions in 2015 with an average acute care

utilization rate of 6.82 visits per year. This study is designed to detect a 20% reduction in the number of acute care encounters per year (assuming a base case of 6 encounters). A 20% reduction in acute care utilization is considered clinically significant based on patient partners reporting that 1 less acute care visit a year is meaningful. Based on a two- sided alpha = 0.05significance level, 67 EA-SCD participants per arm would provide approximately 85% power to detect a 20% reduction in the number of acute care utilizations under individual randomization, assuming the number of encounters follows a Poisson distribution for rare events. The sample size will be inflated based on two parameters: the cluster size coefficient of variation and the intra-class correlation (ICC).⁵⁴ The cluster size coefficient of variation observed among the 14 participating clinical sites is 55%. Therefore, the coefficient of variation is assumed to be 60% and the ICC is assumed to be 0.05.⁵⁶ Based on these parameters, a minimum of 183 EA-SCD participants per arm (366 total EA-SCD participants) will retain approximately 85% power. To account for potential missing data and allow for robust evaluation of secondary endpoints the sample size will be increased to a total of 537 EA-SCD participants. It is estimated that this enrollment can be accomplished with an enrollment rate of 35% of the EA-SCD patient population.

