STATISTICAL CONSIDERATIONS	Estimated average acute care utilization rate for EA-SCD is 6 visits / year. This study is designed to detect a 20% reduction in the number of acute care encounters per year which is considered clinically significant to our patient stakeholders. Based on a two- sided alpha = 0.05 significance level, 67 subjects per arm would provide approximately 85% power to detect a 20% reduction in the number of acute care utilizations under individual randomization, assuming the number of encounters follows a Poisson distribution for rare events. Sample size was inflated based on the cluster size coefficient of variation among our 14 participating clinical sites (55%) and the intra-class correlation (ICC) assumed to be 0.05. Based on these parameters, 183 subjects per arm (366 total subjects) will retain approximately 85% power. The sample size was increased to 537 total EA-SCD subjects to account for potential missing data and allow for robust evaluation of secondary endpoints. It is estimated that this can be accomplished with an enrollment rate of 35% of the EA-SCD patient population.
NUMBER OF EA-SCD PARTICIPANTS	537 total participants will be enrolled Each arm will enroll approximately 269 EA-SCD aged 16 – 25 years
NUMBER OF CLUSTERS	There will be 14 cluster sites, each cluster site comprised of a pediatric SCD clinic, an adult SCD clinic and a SCD CBO. There are 8 large cluster sites with ≥40 EA-SCD currently in pediatrics and 6 small cluster sites with <40 EA-SCD currently in pediatric care. Based on self-reported enrollment targets from each site, 80% of participants will come from large clusters.

SCHEMA

[figure not shown]
Study Schema Figure 1: Overview of Study Design

	Study Schema										
Practices with Emerging Adults with SCD (EA-SCD) aged 16 - 25y Randomized at the Practice Level											
Small Sized Program [≤ 40 EA-SCD] Large Sized Program [> 40 EA-SCD]											
Arm 1- A	Arm 1- B	Arm 2-A	Arm 2-B								
Structured Education Based Transition Program [STE]	Structured Education Based Transition Program [STE] + Peer Mentoring [STE + PM]	Structured Education Based Transition Program [STE]	Structured Education Based Transition Program [STE] + Peer Mentoring [STE + PM]								
	Outcome Meas	ures at 24 Montl	ns								
Primary Outcome: Cha		are visits [ED visits, Adm Hospital Days]	issions, Readmissions at 14d,								

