Transition from pediatrics to adult care is a critical time for EA-SCD. The emergency department (ED) becomes a primary source for care, with ED visits and admissions per year doubling, and avoidable acute care visits rising to account for two-thirds of all SCD hospitalizations. ^{8,11,12} Data from the Healthcare Cost and Utilization Project State Inpatient Databases and State Emergency Department Databases from eight states showed that EA-SCD (18–30y) had the highest acute care utilization rates compared to children 10-17y (3.61 vs 2.04 visits/patient/year). ¹³ The 30-day readmission rate doubled from 27.4% to 48.9% respectively. ¹³ Data from the Registry and Surveillance for Hemoglobinopathies (RuSH) Project cite an increase in acute care utilization rates among EA-SCD (Fig 1). In GA, utilization rose from 0.8 to 3.0/person/year among individuals 10-19y of age compared to those 20 - 49y. ¹⁴ In NC, the average annual acute care visits per person increased from 5 in those <18 years to 12 among 18-35y. ⁴ Disparities also exist with school absenteeism, and EA-SCD miss an average of 20-40 school days/year due to illness, have worse standardized test scores, higher rates of repeat grades and lower overall school attainment compared to controls. ¹⁵ There is limited research to support evidence-based interventions that effectively reduce the high mortality, morbidity, and poor QOL during transition.

Barriers to Transition:

Several identified patient, provider and health system factors contribute to the poor health outcomes of EA-SCD during transition. ¹⁶⁻¹⁸ EA-SCD struggle emotionally with adjusting from a more paternalistic pediatric model to the adult "individualistic" model of care. Adherence to disease modifying treatment drops significantly as they struggle with the developmental maturation process. ¹⁹ Changes or lapses in insurance lead to gaps in comprehensive care -

Version 6: 12/22/2022

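### The stated 85% power at 366 participants relies on normal quantiles for a 14-site comparison; on about 12 degrees of freedom it is about 78%, and section 10.5.4 names no small-sample method

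*Combined protocol and SAP*

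**What the plan says.** Section 10.2 of the combined protocol and SAP sizes the trial in two steps. Under individual randomisation with Poisson counts, 6 visits a year in the control arm and a 20% reduction, it states that "67 EA-SCD participants per arm would provide approximately 85% power" at two-sided 5%. It then allows for seven sites per arm, where "the coefficient of variation is assumed to be 60% and the ICC is assumed to be 0.05", and concludes that "a minimum of 183 EA-SCD participants per arm (366 total EA-SCD participants) will retain approximately 85% power". Enrolment is raised to 537 for missing data and secondary endpoints.

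The synopsis repeats the result ("183 subjects per arm (366 total subjects) will retain approximately 85% power") but ties it to a cluster-size CV of 55%, the observed value, rather than the 60% assumed in 10.2.

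The primary objective (2.1) covers 24 months. Section 10.5.4 specifies a Poisson mixed model with fixed effects for baseline visits, site-size stratum and arm, and a random site effect. It gives no degrees of freedom or other small-sample method. Section 8.2 provides for monthly monitoring of the ICC, without a rule for what follows if it is larger than assumed.

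**The concern.** Sites are randomised, so the evidence on the arm effect comes from 14 site-level results and the error variance is estimated from about 12 degrees of freedom. Normal quantiles treat that variance as known. This raises the stated power. If the analysis uses the same quantiles, it also raises the type I error.

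Secondly, the ICC is applied to a Poisson variance, which fixes a small between-site spread that the protocol never states. Between-site variation largely determines precision with 14 clusters, and adding participants at the same sites does little to reduce it. A null result could then be read against 85% power that the calculation at 366 does not deliver, and a marginally positive one against a 5% error rate that the test does not hold.

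**Working it through.** **Inputs.** From 10.2: two-sided alpha 0.05; rates 6 and 4.8 visits/year (difference 1.2); Poisson variance (sum over arms 10.8); 7 sites per arm; cluster-size CV 0.60, so 1 + CV² = 1.36; ICC 0.05. The calculation below uses one person-year per participant, which is what reproduces the stated 67.

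**1. Reproduce 67.** n = (1.960 + 1.036)² × 10.8 / 1.2² = 67.3.

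**2. Reproduce 183.** With design effect 1 + (1.36m − 1) × ICC and 7 clusters per arm, the mean cluster size is m = 67 × 0.95 / (7 − 67 × 0.05 × 1.36) = 63.65 / 2.444 = 26.04. Then 7 × 26.04 = 182.3, rounded up to 183. With a cluster-size CV of 55% the same formula gives 169, so 183 belongs with 60%.

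**3. Power on normal and t quantiles.**
- At 183 per arm: design effect 1 + (1.36 × 183/7 − 1) × 0.05 = 2.728; SE = √(10.8 × 2.728/183) = 0.401; 1.2/SE = 2.991.
- At 268.5 per arm (537 total): design effect 3.558; SE 0.378; 1.2/SE = 3.172.

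The t columns use the noncentral t distribution, with critical values 2.179 (12 df) and 2.201 (11 df, one further df for the site-size stratum).

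| Total N | Normal | t, 12 df | t, 11 df |
|---|---|---|---|
| 366 | 84.9% | 78.4% | 77.7% |
| 537 | 88.7% | 82.9% | 82.3% |

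**4. Type I error.** If the statistic follows t on 12 df and is compared with 1.96, the error rate is 2 × P(t₁₂ > 1.96) = 7.4%. A simulation of site-level log rates (20,000 runs per setting) with a normal cut-off gave 7.1% to 7.6%.

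**5. Exposure.** Suppose each participant contributes two Poisson person-years. Per-arm variance is then (between-site variance × 1.36 + within-site variance / (2m)) / 7, with m = N/14, summed over arms.
- Between-site variance 0.05 × rate and within-site variance 0.95 × rate in each arm: t power (12 df) 85.5% at 366 and 87.8% at 537.
- A constant site CV of 9.1% in both arms with within-site variance equal to the rate: 87.5% and 89.9%.

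So the range is about 86–88% at 366 and 88–90% at 537.

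**6. Site spread implied by the ICC.** √(0.05 × 6) = 0.55 visits/year, a CV of 9.1%. If 6 is taken as the within-site variance, √(6 × 0.05/0.95) = 0.56, a CV of 9.4%. Either way, about 95% of sites would lie between 4.9 and 7.1 visits/year.

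**7. Sensitivity to the site CV (assumed values).** Same variance form as step 5, 537 enrolled, t on 12 df. The low end of each range uses one person-year and the 1.36 penalty for unequal sites; the high end uses two person-years and equal site weights.
- CV 15%: variance from (0.0225 × 59.04 × 1.36 + 10.8/38.36)/7 = 0.298, power 52%, to (0.0225 × 59.04 + 10.8/76.71)/7 = 0.210, power 67%. Here 59.04 = 6² + 4.8².
- CV 20%: 35% to 46%.

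**The case against.** **Follow-up is longer than one year.** This stands in part. The objective spans 24 months, and step 5 shows that two person-years restore 85% on t quantiles. A reader might infer from 78% that the design cannot reach 85% under its own assumptions; that goes too far. But 10.2 does not state that exposure, and the recovery needs both truly Poisson counts and a site CV near 9%.

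**Planned enrolment is 537.** At 83% the shortfall there is about two points, which is modest. Section 10.2, however, assigns the extra participants to missing data and secondary endpoints and makes its 85% claim at 366.

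**Regional rates.** Section 1.1 reports that "In GA, utilization rose from 0.8 to 3.0/person/year among individuals 10-19y of age compared to those 20 - 49y" and that "In NC, the average annual acute care visits per person increased from 5 in those <18 years to 12 among 18-35y". A reader might infer a site CV far above 9%, and hence power of 50% or less. The documents do not support that. These figures mix age bands and sources, and the trial enrols ages 16–25. The three rates that 10.2 itself cites for sizing (6, 6.82 and 7.17) have a CV of 9.0%, though three area-level figures do not establish a site CV either. Baseline adjustment may also remove some site variation, for which 10.2 takes no credit.

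**The 9% comes from the Poisson variance.** Correct. With the SD of 8.5 around a mean of 5.3 given in 1.1 for the oldest age group, the same ICC implies a site SD of √0.05 × 8.5 = 1.9 visits/year, a CV of 36%. The small spread is thus a consequence of the variance model and is not evidence that 0.05 is a wrong ICC.

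**The ICC is monitored.** True, and nothing in 8.2 says that the monitored ICC assumes a Poisson variance. What is missing is the between-site CV itself, which can be read directly against the power calculation.

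**Conclusion.** The point holds as one of method and sensitivity. The arithmetic in 10.2 is not wrong: 183 reproduces. But the approximately 85% at 366 depends on normal quantiles. With the protocol's inputs, one person-year and 12 df, power is about 78% at 366 and 83% at 537 (78% and 82% on 11 df). The lack of a small-sample method in 10.5.4 matters at least as much, because it leaves open a type I error of about 7.4% in place of 5%.

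The site CV of about 9% is an unstated assumption without site-level support. It is not a demonstrated error, and the power figures at 15% and 20% rest on assumed CVs.

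**What to change.** No added participants or sites.

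1. In 10.5.4, test the arm effect with a method suited to 14 clusters: t or F with between-site df of about 11–12, a site-level analysis, or a permutation test. A permutation test should respect the stratification and the same-arm constraint in 4.2.
2. In 10.2 and the synopsis, restate power on that basis (about 78% at 366 and 83% at 537 on one person-year) and state the exposure assumed. If two person-years are claimed, give about 86–88% and 88–90% with the conditions attached. Pair 183 with the 60% cluster-size CV in both places.
3. Add a line of power over residual between-site CVs, labelled as assumed: at 537 on t with 12 df, about 52–67% at CV 15% and 35–46% at CV 20%.
4. In the existing 8.2 monitoring, report the between-site CV of visit rates alongside the ICC.

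The cost is a less favourable stated power and a confidence interval about 11–12% wider than one built on 1.96 (2.179/1.960 = 1.11; 2.201/1.960 = 1.12). The rest is protocol and SAP wording.
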